11.2.2.2 Time to Disease Resolution (Symptoms Resolution and Viral Clearance)

Time to disease resolution that is defined as both viral clearance (two consecutive negative diagnostic tests) and symptoms resolution (new onset COVID-19 symptoms resolved, and pre-existing symptoms returned to baseline) through Day 28 will be analyzed as similarly to that described for time to disease resolution that is defined as symptoms resolution. Participants who have completed Day 21 visit but not Day 35 visit and did not have two consecutive negative tests at the time of study stop will be censored at the time of their last visit.

11.2.2.3 Subgroup Analysis

Analysis of key secondary endpoints will be repeated for the subgroups as specified in Section 11.1.3. Forest plots will be provided.

11.2.3 Proportion of Participants with Disease Resolution

The proportions of participants who achieve disease resolution defined as symptom resolution at Days 8, 14, 21, and 28 will be summarized for the study intervention and control. The 2-sided 95% CI for the proportion will be computed using the Mid-p method. The absolute difference in the proportion and the corresponding 2-sided 95% CI of participants achieving disease resolution defined as symptom resolution at any time up to and including Days 8, 14, 21, and 28 between the study intervention and control will be assessed using the stratified Miettinen and Nurminen method, stratified by number of days of symptoms at time of randomization (<6 days or ≥ 6 days).

In addition, the proportions of participants who achieve disease resolution defined as symptom resolution and viral clearance (2 consecutive negative diagnostic tests) at any time up to and including Days 8, 14, 21, and 28 will be summarized and analyzed as similar to that described for the proportions of participants who achieve disease resolution defined as symptom resolution only.

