**Table 3: Objectives and Endpoints**

Objectives	Endpoints
Primary	
To characterize safety of study intervention	
Through Day 35
 
 
• Frequencies of grade 3 AEs and grade 4 AEs
 
• AEs resulting in study intervention discontinuation
 
• All SAEs
 

To assess efficacy of study intervention	
 
• Proportion of participants who progress to moderate or severe disease category or higher (Gates MRI ordinal scale <math>\geq 3</math>) through Day 28
 

Secondary	
To assess clinical efficacy of study intervention	
 
• Time to disease resolution, defined as BOTH viral clearance (two consecutive negative diagnostic tests) and symptoms resolution (new onset COVID-19 symptoms resolved, and pre-existing symptoms returned to baseline*) through Day 28
 
• Time to disease resolution, defined as symptoms resolution only (new onset COVID-19 symptoms resolved, and pre-existing symptoms returned to baseline*) through Day 28
 
• Proportion of participants who progress to moderate or severe disease category or higher (Gates MRI ordinal scale <math>\geq 3</math>) at Days 8, 14 and 21
 
• Proportion of participants who achieve disease resolution at Days 8, 14, 21 and 28
 
• Gates MRI scale score at Days 8, 14, 21 and 28
 
• WHO ordinal scale score at Days 8, 14, 21 and 28
 
• Incidence and number of days of hospitalization at Days 8, 14, 21 and 28
 

Exploratory objectives	
To assess virological efficacy	
 
• Quantity (and change from baseline) of SARS-CoV-2 virus at Days 8, 14, 21 and 28
 

To assess viral sequence	
 
• Phylogenetic relationships of SARS-CoV-2 viruses sequenced from positive nasal swab samples
 

\*Baseline refers to health status prior to contracting COVID-19.

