5 TRIAL OBJECTIVES

The following objectives and associated endpoints are part of this study.

Table 1: Study objectives and associated endpoints.

| Objectives | Endpoints |
|---|--|
| Primary | |
| To characterize safety of study intervention | Through Day 35 
 • Frequencies of grade 3 adverse events (AEs) and grade 4 AEs • AEs resulting in study intervention discontinuation • All SAEs |
| To assess efficacy of study intervention | 
 • Proportion of participants who progress to moderate or severe disease category or higher (Gates MRI ordinal scale ≥ 3) through Day 28 |
| Secondary | |
| To assess clinical efficacy of study intervention | 
 • Time to disease resolution, defined as symptoms resolution only (new onset COVID-19 symptoms resolved, and pre-existing symptoms returned to baseline*) through Day 28 • Time to disease resolution, defined as both viral clearance (two consecutive negative diagnostic tests) and symptoms resolution (new onset COVID-19 symptoms resolved, and pre-existing symptoms returned to baseline*) through Day 28. • Proportion of participants who progress to moderate or severe disease category or higher (Gates MRI ordinal scale ≥ 3) at Days 8, 14 and 21 • Proportion of participants who achieve disease resolution, defined as symptoms resolution only, at Days 8, 14, 21 and 28 • Proportion of participants who achieve disease resolution, defined as both viral clearance and symptoms resolution, at Days 8, 14, 21 and 28 • Gates MRI scale score at Days 8, 14, 21 and 28 • World Health Organization (WHO) ordinal scale score at Days 8, 14, 21 and 28 • Incidence and number of days of hospitalization at Days 8, 14, 21 and 28 |
| Exploratory | |
| To assess virological efficacy | 
 • Quantity (and change from baseline) of SARS CoV-2 virus at Days 8, 14, 21 and 28 |
| To assess viral sequence | 
 • Phylogenetic relationships of SARS-CoV-2 viruses sequenced from positive nasal swab samples |

*Baseline refers to health status prior to contracting new onset COVID-19 symptoms.

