11.2.1 Estimand

The treatment policy estimand with respect to the secondary efficacy objective is defined for the key secondary endpoints by the following:

Population: Participants in the ITT population.

Patient-level outcome: Time to disease resolution through day 28.

Intercurrent events: The following intercurrent events to be taken into account:

1. If a death occurs prior to Day 28, the participant will be considered as not having disease resolution through Day 28 (i.e., censored at Day 28).
2. If a participant is lost to follow-up prior to Day 28, the participant will be considered as not having disease resolution and will be censored at the time of lost to follow-up.
3. If a participant discontinues the study [for any reason: lost to follow-up, progression to moderate or severe COVID-19 (or worse), withdrawal of consent] prior to initiation of IP dosing on Day 1 and no symptoms resolution assessment is available, the participant will be considered as not having disease resolution and will be censored on Day 1.

Participants who discontinue study intervention will be followed at least until end of study, Day 35.

Population-level summary measure: Median time to disease resolution.

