11.2.2 Disease Resolution

11.2.2.1 Time to Disease Resolution (Symptoms Resolution)

Disease resolution is defined as symptoms resolution (new onset coronavirus disease 2019 (COVID-19) symptoms resolved, and pre-existing symptoms returned to baseline) through Day 28. For the time to disease resolution analysis, the following hypothesis will be tested: prophylactic treatment with rivaroxaban will increase the rate of time to disease resolution relative to placebo in high risk participants with mild COVID-19.

Time to disease resolution is defined as the time from first dose to the date of symptoms resolution (as determined by the investigator: has the participant’s COVID-19 signs and/or symptoms resolved or returned to baseline). The following rules (Table 3) will be used to define time to disease resolution:

Table 3: Censoring rules for time to disease resolution.

| Situation | Outcome | Date of event/censoring |
|---|----------|--|
| Death for any reason | Censored | Day 28 |
| Discontinued prior to Day 28 without disease resolution | Censored | Date of last disease resolution assessment |
| No disease resolution through Day 28 | Censored | Day 28 |
| Randomized, treated but no post-baseline assessments available | Censored | Day 1 |
| Disease resolution through Day 28 | Event | Initial date of last sequence of consecutive disease resolution. |
| Discontinued prior to Day 28 with disease resolution at last assessment | Event | Initial date of last sequence of consecutive disease resolution. |
| Randomized, not treated | Censored | Date of randomization |

*sequence = a series of one or more disease resolutions with no progression.

Example scenarios are included in Table 4 for reference.

Table 4: Example scenarios for time to time to disease resolution.

| Time point | Day 1 | Day 4 | Day 6 | Day 8 | Day 10 | Day 12 | Day 14 | Day 18 | Day 21 | Day 24 | Day 28 | Endpoint |
|----------------|-------|-------|-------|-------|--------|--------|--------|--------|--------|--------|--------|-----------------------------|
| Participant 1 | N | N | N | N | N | N | N | N | N | N | N | No DR, censored at Day 28 |
| Participant 2 | N | Y | N | N | N | N | Died | | | | | No DR, censored at Day 28 |
| Participant 3 | N | Y | Y | N | N | N | Disc. | | | | | No DR, censored at Day 12 |
| Participant 4 | N | Y | N | N | N | Y | Y | Y | Y | Y | N | DR at Day 12* |
| Participant 5 | N | Y | Y | N | N | Y | Y | Y | Disc. | | | DR at Day 12 |

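### Taken literally, SAP 11.2.3 counts any single resolved visit as disease resolution for good, whereas 11.2.1 and Tables 3 and 4 class participants who then die, or relapse without recovering, as not resolved

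*SAP*

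**What the plan says.** **Proportion analysis (SAP 11.2.3).** The descriptive sentence for symptom-only resolution has a visit-day basis: "The proportions of participants who achieve disease resolution defined as symptom resolution at Days 8, 14, 21, and 28 will be summarized". The between-arm difference has a cumulative basis: "at any time up to and including Days 8, 14, 21, and 28 between the study intervention and control". The composite with viral clearance is also cumulative: "2 consecutive negative diagnostic tests) at any time up to and including Days 8, 14, 21, and 28 will be summarized". The section gives no rule for death or relapse and does not cite Table 3 or Table 4.

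**Time-to-event analysis of the same endpoint.**
- SAP 11.2.1, on death: "If a death occurs prior to Day 28, the participant will be considered as not having disease resolution through Day 28". Participants lost to follow-up before Day 28 are likewise treated as not resolved, and are censored.
- SAP Table 3 dates the event at the "Initial date of last sequence of consecutive disease resolution" and censors deaths at Day 28.
- SAP Table 4 labels a participant No DR when consecutive unresolved visits follow resolved ones.

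**Endpoint definitions.** Protocol Table 3 has "Proportion of participants who achieve disease resolution at Days 8, 14, 21 and 28", and SAP Table 1 has "Proportion of participants who achieve disease resolution, defined as symptoms resolution only, at Days 8, 14, 21 and 28". Protocol 10.5.1 speaks of each time point through Day 28. SAP section 8 declares no change from the protocol.

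**The concern.** A cumulative count suits an event that is meant to stand once it has happened, such as progression or hospitalization. Symptom resolution can reverse, and the SAP wrote Tables 3 and 4 to handle that. Section 11.2.3 does not use those rules. Two secondary analyses of one endpoint could therefore classify the same participant differently, including someone who died and is reported in one of them as having achieved resolution.

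Within 11.2.3, the symptom-only proportions by arm and their difference rest on differently worded time bases, so the difference need not equal the gap between the displayed proportions. A programmer would have to choose a definition with the data in hand.

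**Working it through.** **Inputs.** The 12 visit patterns and endpoints in SAP Table 4, the rules in SAP Table 3 with the two Table 4 footnotes, and the wording of 11.2.3.

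| Participant | Visits scored resolved | Other course | Table 4 endpoint | First resolved visit |
|---|---|---|---|---|
| 1 | none | unresolved throughout | No DR, censored Day 28 | none |
| 2 | Day 4 | unresolved Days 6–12, then died | No DR, censored Day 28 | Day 4 |
| 3 | Days 4, 6 | unresolved Days 8–12, then discontinued | No DR, censored Day 12 | Day 4 |
| 4 | Days 4, 12–24 | unresolved Days 6–10 and 28 | DR Day 12 | Day 4 |
| 5 | Days 4, 6, 12–18 | unresolved Days 8–10; discontinued after Day 18 | DR Day 12 | Day 4 |
| 6 | Days 6, 8, 14–28 | unresolved Days 10–12 | DR Day 14 | Day 6 |
| 7 | Day 28 | unresolved until then | DR Day 28 | Day 28 |
| 8 | Days 12–21 | unresolved Days 24, 28 | No DR, censored Day 28 | Day 12 |
| 9 | Day 4 | no data afterwards | DR Day 4 | Day 4 |
| 10 | none | no data after Day 1 | No DR, censored Day 1 | none |
| 11 | all visits | none | DR Day 1 | Day 1 |
| 12 | Days 4, 12, 14 | unresolved Days 6–10 and 18, then discontinued | No DR, censored Day 18 | Day 4 |

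**Step 1: reproduce the plan.** Applying Table 3 and the two footnotes to the patterns returns all 12 stated endpoints. Six of 12 have resolution through Day 28 (4, 5, 6, 7, 9, 11).

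**Step 2: count under each definition.**
- Literal 11.2.3: first resolved visit on or before Day X.
- Table 3: event date on or before Day X.
- Visit day: scored resolved at the Day X visit itself.

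| Day | Literal 11.2.3 | Table 3 date | Visit-day status | Literal only, not Table 3 |
|---|---|---|---|---|
| 8 | 8 | 2 | 2 | 2, 3, 4, 5, 6, 12 |
| 14 | 9 | 5 | 6 | 2, 3, 8, 12 |
| 21 | 9 | 5 | 4 | 2, 3, 8, 12 |
| 28 | 10 | 6 | 3 | 2, 3, 8, 12 |

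At Day 28 the gap is 10 − 6 = 4: one death (Participant 2) and three relapses without recovery (3, 8, 12). At Day 8 the gap is 8 − 2 = 6, because Participants 4, 5 and 6 also count early although their event dates are Days 12, 12 and 14.

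**Step 3: what follows for the arms.** A Table 3 event date is itself a resolved visit, so anyone resolved by Day X under Table 3 is also resolved under the literal rule. In each arm the literal proportion is therefore at least as large. Write e for the fraction of an arm resolved only under the literal rule. Then

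risk difference (literal) − risk difference (Table 3) = e(rivaroxaban) − e(placebo).

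The documents give no relapse or death rates by arm, so neither the sign nor the size of this quantity can be stated.

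**The case against.** **The cumulative wording may be shorthand.** The SAP uses the same kind of phrase for the primary endpoint, earlier progression and hospitalization. Section 11.2.3 follows directly after the section that dates resolution. It could mean a Table 3 event dated on or before Day X, and then there is no conflict. This reading is possible, but the SAP does not write it, and the literal reading needs no added words.

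**The death rule may already apply.** SAP 11.2.1 introduces its estimand for the secondary efficacy objective. However, the outcome it then lists is time to disease resolution, so its reach to the proportions is uncertain.

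**Table 3 is not a strict standard of sustained recovery.** This stands. A sequence may consist of a single resolved visit: Participants 7 and 9 count on one. Participant 4 is unresolved at the last visit and still counts. A reader might infer that every relapse is misclassified, but Participants 4, 5 and 6 relapse and are resolved by Day 28 under both rules.

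**Harm to the comparison is not shown.** This also stands. A reader might infer that the literal rule hides a treatment effect. Raising both proportions can shrink, preserve or enlarge their difference, and no figure in the documents settles which.

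**Table 3 dating is one choice among three.** It looks ahead: Participant 6 is resolved at the Day 8 visit, and Participants 8 and 12 at Day 14, yet none of them would count on those days. That is a reason to label the alternatives, not to leave the definition open.

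**Conclusion.** The point holds as a conflict of definitions. Followed as written, 11.2.3 counts as resolved a participant who dies and participants who relapse without recovering, whom 11.2.1 and Tables 3 and 4 class as not resolved. The visit-day wording elsewhere adds a third definition, so the same 12 examples give 10, 6 or 3 resolved at Day 28.

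Table 4 is a set of illustrative scenarios, so these counts prove the conflict and do not estimate its size in the trial. The conclusion assumes the literal reading. If the sponsor meant the Table 3 date, the defect is a missing cross-reference and missing rules for death and censoring. The affected analyses are secondary; the primary endpoint does not depend on them. The correction should be made.

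**What to change.** In SAP 11.2.3, for both the arm proportions and their difference:
- Define resolved by Day X as a Table 3 event date on or before Day X.
- Count deaths before Day 28 as not resolved at every cut-off, in line with 11.2.1.
- Keep participants censored before Day X without an event in the ITT denominator as not resolved, also in line with 11.2.1. This must be stated, because the default in SAP 9.2 limits denominators to participants with non-missing data.
- Apply the same rule to the composite with viral clearance. SAP 11.2.2.2 censors some participants only because the study stopped, so report their number by arm beside the Day 28 composite.
- Label any visit-day or ever-resolved summary as a separate descriptive analysis.

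The cost is a few sentences in the SAP and no new data. The reported proportions will be lower than under the literal wording, and some participants who are resolved at a given visit will not count on that day because of what happened later.

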11.2.4 Disease Progression of COVID-19

The proportion of participants who progress to moderate or severe disease category or higher (Gates MRI ordinal scale ≥ 3) at any time up to and including Days 8, 12, and 21 will be summarized and analyzed for the study intervention and control as similar to that described for proportion of participants who progress to moderate or severe disease category or higher through Day 28.

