## **9.2. Procedures at Visits from Day 4 through Day 28**

At each of these visits on Days 4, 6, 8, 10, 12, 14, 18, 21, 24, 28, the study staff conducting the visit will:

- Introduce themselves, explain their role to the participant, and confirm the identity of the participant
- Confirm that the means of contact is adequate to conduct the contact/visit
- Collect information on COVID-19 symptoms and signs
- Assess the Gates MRI and WHO ordinal scales
- Collect information on AEs
- Collect information on bleeding events and severity
- Collect information on concomitant medications
- Remind the participant to take the dose daily through Day 21, and not to show the study IP tablets or describe the tablets detailed appearance, to maintain the masking of the study staff.
- Collect information on adherence to study IP and any dosing error (if applicable)
- Ask participant to collect temperature, and oxygen saturation during the encounter (study staff will document temperature and oxygen saturation)
- Ask participant to collect nasal sample during the encounter for Days 4, 8, 14, 21 and 28
- Inquire about pregnancy, as appropriate.

As needed, additional contact with the study clinician or staff will be conducted at the request of the participant (e.g., if developing concerning symptoms or an AE).

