8 CHANGES IN CONDUCT OR PLANNED ANALYSES FROM THE PROTOCOL

Not applicable.

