11 EFFICACY PARAMETERS

The primary efficacy endpoint is the proportion of participants who progress to moderate or severe disease category or higher (Gates MRI ordinal scale ≥ 3) at any day through Day 28.

Secondary efficacy endpoints include:

- Time to disease resolution, defined as symptoms resolution only (new onset COVID-19 symptoms resolved, and pre-existing symptoms returned to baseline) through Day 28
- Time to disease resolution, defined as both viral clearance (two consecutive negative diagnostic tests) and symptoms resolution (new onset COVID-19 symptoms resolved, and pre-existing symptoms returned to baseline*) through Day 28
- Proportion of participants who progress to moderate or severe disease category or higher (Gates MRI ordinal scale ≥ 3) at Days 8, 14, and 21
- Proportion of participants who achieve disease resolution, defined as symptoms resolution only, at Days 8, 14, 21 and 28
- Proportion of participants who achieve disease resolution, defined as both viral clearance and symptoms clearance, at Days 8, 14, 21 and 28
- Gates MRI scale score at Days 8, 14, 21, and 28
- WHO ordinal scale score at Days 8, 14, 21, and 28
- Incidence of hospitalization through Days 8, 14, 21, and 28
- Number of days of hospitalization through Days 8, 14, 21, and 28

Exploratory endpoints include:

- Quantity (and change from baseline) of SARS-CoV-2 virus at Days 8, 14, 21 and 28
- Phylogenetic relationships of SARS-CoV-2 viruses sequenced from positive nasal swab samples

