11.2.5 Gates MRI Scale Scores

Table 5: Gates MRI Ordinal Scale Clinical Endpoint Definitions

| Scale | Category | Endpoint definition |
|-------|---|---|
| 1 | Asymptomatic/symptoms similar to pre-COVID-19 status | 
 No symptoms and signs AND No limitation of daily activities |
| 2 | Mild | 
 Symptomatic AND No shortness of breath AND No hypoxemia (O_2 saturation $\geq 94\%$ in ambient air) |
| 3 | Moderate or severe | 
 Symptomatic AND Shortness of breath* OR tachypnea (respiratory rate ≥ 20 min)* OR hypoxemia ($< 94\%$ in ambient air)* |
| 4 | Critically ill | 
 Symptomatic AND Receiving high flow oxygen OR non-invasive mechanical ventilation |
| 5 | Critically ill with invasive mechanical ventilation or extra pulmonary complication | 
 Symptomatic AND Receiving invasive mechanical ventilation OR Life threatening or debilitating extra pulmonary complications |
| 6 | Critically ill with Extra-Corporeal Membrane Oxygenation (ECMO) | 
 Symptomatic AND Receiving ECMO |
| 7 | Death | 
 Death |

*For known COPD participants, moderate or severe category requires worsening of shortness of breath or medical or oxygen saturation from pre-COVID-19 status.

The distributions of the Gates MRI ordinal scale scores (defined as in Table 5) will be summarized by day and treatment group. Stacked bar plots presenting the proportion of participants in each category of Gates MRI ordinal scale at Days 8, 14, 21, and 28 for each treatment group will be provided.

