11.2.7 Incidence of Hospitalization

The proportion of hospitalized participants at any time up to and including Days 8, 14, 21, and 28 will be summarized for the study intervention and control with the corresponding 2-sided 95% CIs computed using the Mid-p method. The risk ratios and the corresponding 2-sided score 95% CIs associated with the incidence of hospitalization for the study intervention relative to control at any time up to and including Days 8, 14, 21, and 28 will be assessed using the stratified CMH method, stratified by number of days of symptoms at time of randomization (<6 days or ≥6 days).

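### SAP 11.2.4 names Day 12 where every dated definition of the secondary progression endpoint names Day 14

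*SAP*

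**What the plan says.** Protocol Table 3 lists, as a secondary endpoint, the proportion of participants progressing to Gates MRI scale 3 or higher "at Days 8, 14 and 21". SAP Table 1 repeats those days, and the endpoint list in SAP Section 11 again has "at Days 8, 14, and 21".

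SAP Section 11.2.4 gives the method. It takes progression "at any time up to and including Days 8, 12, and 21" and refers back to the primary analysis. That means a proportion with a mid-p interval per arm, and a Miettinen-Nurminen risk difference stratified by days since symptom onset.

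The other cumulative secondary analyses use Day 14. Disease resolution (SAP 11.2.3) is taken "at any time up to and including Days 8, 14, 21, and 28", and SAP 11.2.7 has "The proportion of hospitalized participants at any time up to and including Days 8, 14, 21, and 28". SAP Section 8, which is meant to record changes from the protocol's planned analyses, reads "Not applicable".

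**The concern.** The endpoint is defined on one set of days and its analysis is specified on another. The tables are programmed from the methods section, and that is where the odd day sits. If 11.2.4 is followed as written, the report contains a comparison at a time point that no objective names. It lacks the planned comparison at a time point that both documents list. A SAP should settle this before the results are seen, not leave it to whoever programs the table.

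**Working it through.** The core of this point needs no sample size, power or event count. The check is a comparison of the texts.

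| Place | What it does | Days |
|---|---|---|
| Protocol Table 3 | defines the progression endpoint | 8, 14, 21 |
| SAP Table 1 | defines the progression endpoint | 8, 14, 21 |
| SAP Section 11 | defines the progression endpoint | 8, 14, 21 |
| SAP 11.2.4 | analyses the progression endpoint | 8, 12, 21 |
| SAP 11.2.3 | analyses disease resolution | 8, 14, 21, 28 |
| SAP 11.2.5 | plots Gates MRI scale categories | 8, 14, 21, 28 |
| SAP 11.2.7 | analyses hospitalization | 8, 14, 21, 28 |

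**1. The mismatch.** Defined days {8, 14, 21} against analysed days {8, 12, 21}: Day 14 is defined but has no specified analysis, and Day 12 is analysed but not defined. One of three time points is affected.

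**2. Is it a declared change?** The SAP document history itemises the changes in Versions 1.2 and 2.0. None moves a progression time point. SAP Section 8 declares nothing either, but its silence is weaker evidence, since it also omits the dropped models that the history does list. With three matching definitions and three neighbouring sections on Day 14, a typing slip is the natural explanation.

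**3. Would the error show itself?** Probably not from the data. Protocol 9.2 schedules scale assessments "At each of these visits on Days 4, 6, 8, 10, 12, 14, 18, 21, 24, 28", so both Day 12 and Day 14 are scored visits. Protocol Table 1 and SAP Appendix 1 agree. A Day 12 table would be complete and look plausible.

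**4. Does another output supply Day 14?** SAP 11.2.5 offers "Stacked bar plots presenting the proportion of participants in each category of Gates MRI ordinal scale at Days 8, 14, 21, and 28". That is status on the day, with no treatment difference or interval. Take a participant who reached scale 3 at Day 8 and was back at scale 1 or 2 by Day 14. The cumulative analysis counts that participant as progressed; the Day 14 distribution does not show it.

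**5. What happens to events between the two visits?** The analysis is cumulative, so those progressed by Day 12 are a subset of those progressed by Day 14, then by Day 21, then by Day 28. A participant who first reaches scale 3 after Day 12 and by Day 14 is absent from the Day 12 result but present at Day 21 and in the primary analysis. No event leaves the progression analyses; one intermediate cut moves back by one scheduled visit.

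**The case against.** The strongest reply is that the SAP twice lists Day 14 for this endpoint, so a careful statistician would notice the conflict and analyse Day 14 anyway. That is fair as far as it goes. A reader might infer that Day 14 will certainly go unanalysed, and the documents do not support that: the instructions conflict, and omission is a risk. The conflict still stands, because 11.2.4 is the only section giving the method.

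It can also be said that the stakes are low, and they are. SAP 11.2.1 frames its key secondary estimand around time to disease resolution, not this endpoint. Neither document assigns this endpoint a share of alpha or a multiplicity procedure. The trial had already stopped for futility.

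Two stronger readings are tempting and should be resisted.

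- **That the gap falls in the peak-risk period.** Protocol 3.2.2.1 puts likely progression at Days 8-12 of illness, counted from symptom onset. SAP 9.2 counts study days from first dose. Study Days 12 to 14 are 11 to 13 days after first dose. With onset on the day of first dose, that is 11 to 13 days after onset. With the protocol's worst case of about 9 days from onset to first dose, it is 9 + 11 = 20 to 9 + 13 = 22 days. The interval therefore lies at or beyond the end of the cited period. The documents give no event count for it.
- **That Day 12 was chosen after seeing data.** SAP Version 2.0 is dated 11 February 2021, after the futility finding of 3 February, so a reader might wonder. The documents do not show when the 12 entered the text. The SAP states that the sponsor stayed blinded, and the surrounding sections point to a clerical error. Nothing supports selection.

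**Conclusion.** The inconsistency is real and sits in the current SAP text. SAP 11.2.4 is wrong against both the protocol and the SAP's own endpoint lists. Followed literally, it would leave the secondary progression endpoint without its comparative analysis at Day 14.

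Its reach is small: one intermediate time point out of three, for one secondary endpoint. The primary endpoint through Day 28, the sample size, the futility rule and the safety analyses are untouched. How far a Day 12 result would differ from a Day 14 result cannot be derived from the documents.

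The conclusion assumes that 11.2.4 is the operative instruction for programming this endpoint. No other section gives its method.

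**What to change.** In SAP 11.2.4, change 12 to 14 so that the days read 8, 14 and 21. If Day 12 was in fact intended, declare it with a reason in SAP Section 8 and align SAP Table 1 and the Section 11 endpoint list, so that the departure from Protocol Table 3 is visible. If the SAP can no longer be amended, analyse Day 14 as defined and record the discrepancy in the clinical study report, where Protocol 11.5 already requires deviations from planned analyses to be described.

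The cost is one number in the SAP and the matching table shell. No new data are needed, because Day 14 scoring is already in the schedule.
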